#### **4.3 Subject Recruitment and Consent**

Study staff will recruit subjects via word of mouth to friends, family and colleagues. Those who are interested will schedule Visit 1 with study staff, where the informed consent discussion and determination of eligibility will take place. Those who are eligible will have Visit 2 scheduled.

#### **4.4 Subject Compensation**

Subjects will be compensated \$15 for Visit 1 and \$100 each for Visits 2 and 3. They will be mailed a check through UAMS SAP for their amount based upon visits attended.

#### **4.5 Study Visits**

Visit 1: This visit will take place at the UAMS RIOA.

At this visit, informed consent discussion is held. Study staff will use appropriate PPE with surgical mask and gloves. Subjects will also be required to wear a mask and if they do not have one, a mask will be provided to them by the study staff. If a subject enrolls, their eligibility will be determined. Eligible subjects will be randomized and be scheduled for Visit 2. A whole body DXA scan will be performed by study staff using the PI's machine for quantification of lean mass.

Visit 2: This visit will take place at the UAMS IOA. Subjects will be instructed to fast (consuming only water) from 10:00 P.M. the evening prior to this visit. Study nurse will insert an IV into the subject's preferred arm. At scheduled intervals, study staff will draw a ~2mL blood sample from the IV for research purposes, warming the arm by means of a heating pad or a heated plastic box. Blood will be transferred into a blood collection tube that contains EDTA, cooled on wet ice, centrifuged at  $\geq$  3000 RPM for  $\geq$  6 minutes, and have the resultant plasma transferred to a labelled cryo tube for freezing at  $\leq$  -80 degrees Centigrade.

After the initial blood sample is drawn, subjects will begin ingesting their oral isotope preparations, beginning with a priming dose (per study-specific stable isotope calculations). A timer will start when the priming dose is ingested. At 10-minute intervals, subjects will ingest a smaller volume of stable isotope preparations that will continue throughout the duration of the study visit (approximately 7 hours).

Approximately three hours after study initiations, subjects will ingest their randomly chosen amount of SP. Blood sample collection will continue at specific intervals throughout the remainder of Visit 2.

At the conclusion of the 7-hour study visit, the IV will be removed and a bandage placed over the site. Subjects will be provided with snacks and a beverage and be free to leave the site. Visit 3 is scheduled.

Visit 3: Subjects will come back to the RIOA having fasted overnight as for Visit 2. All study procedures undertaken during Visit 2 will be repeated at Visit 3, with subjects ingesting the remaining SP amount.

#### **4.6 Blinding**

This will be a double-blinded study. Both SP amounts are dissolved into equal volumes of water so that subjects will not know which amount they are ingesting. Blood samples are coded so that lab staff and investigators will not know which amount of SP was consumed at each visit. Investigators will be unblinded after all samples have been processed and data analysis has taken place.

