#### **4.7 Randomization**

SP grouping will be predetermined before the first enrollment takes place. Study staff will document enrollment information into a spreadsheet that contains the SP group designations. SP labels will contain these designations. In the event that subject dropouts or screening failures skew the balance of groups, the groups will be modified toward the end of the enrollment period so that balance will be regained at the conclusion of the study.

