#### **4.8 Study Products**

SP arrives packaged in a small tub. It is stored at room temperature. Study staff will weigh the doses of SP: 6.3g and 12.6g. Prior to ingestion, SP is dissolved into approximately 120mL of cool water. This product has been approved and used in previously approved studies (IRB#217658). It is provided at no cost by Adesso, LLC (Delaware).

---

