## **5.3 Sample Analysis**

Plasma samples are analyzed for amino acid concentrations and stable isotope levels (enrichment). The analyses are performed in the CTRAL by study staff.

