## **5.7 Data Access**

All study subject material will be assigned a unique identifying code or number. The key to the code (the instrument associating the data with subject identity) will be kept on a password protected UAMS server, located behind locked doors in a restricted access area of the UAMS campus. Only those individuals listed on the title page of this protocol and their research staff members will have access to the code and information that identifies the subject in this study. This file will be deleted approximately seven years after data analysis is completed.

---

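### Does the lack of a documented separation between staff who know the dose and staff who assay samples undermine the double blind?

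*Combined protocol and SAP*

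**What the plan says.** Section 4.6 calls the study double-blind. Subjects are blinded by dissolving both amounts in equal volumes of water. For everyone else the only safeguard named is coding: "Blood samples are coded so that lab staff and investigators will not know which amount of SP was consumed at each visit". On timing it says: "Investigators will be unblinded after all samples have been processed and data analysis has taken place".

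Other sections assign the steps that touch dose or identity:

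- 4.7, allocation: "Study staff will document enrollment information into a spreadsheet that contains the SP group designations. SP labels will contain these designations".
- 4.8, preparation: "Study staff will weigh the doses of SP: 6.3g and 12.6g". Section 6.4 adds that study staff dispense and account for the product.
- 5.3, assays: "The analyses are performed in the CTRAL by study staff".
- 5.7, code key: "Only those individuals listed on the title page of this protocol and their research staff members will have access to the code". The same section describes the key as linking data to subject identity.

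If dropouts or screening failures upset the balance, 4.7 says that "the groups will be modified toward the end of the enrollment period so that balance will be regained at the conclusion of the study". It gives no rule and names nobody to apply one. Recruitment is informal (4.3): "Study staff will recruit subjects via word of mouth to friends, family and colleagues".

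**The concern.** Read together, these sections seem to defeat the coding in 4.6. The 5.7 key leads from sample to subject, and the 4.7 spreadsheet leads from subject to dose order. Someone with both files knows the dose at each visit, and whoever weighs the product knows it anyway. No passage keeps such a person away from the assays or from the calculation of protein synthesis (PS), breakdown (PB) and net balance (NB).

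This could matter because SA1 sets each oral dose against infusion values already determined for the same product and dosing. A person who knows the dose knows the value the oral result is hoped to match. Each visit yields 15 samples (5.1), and 5.4 does not say which enter the average or when one may be left out. Choices among samples could then favour a finding of validity. Late regrouping looks like a second weakness, since somebody must see the orders during enrolment to know that they have become unbalanced.

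**Working it through.** The plan gives no figure for this point, so there is none to reproduce. The check has three parts.

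**1. What the text establishes.** 4.6 names lab staff and investigators as distinct groups, and 4.5 has a study nurse place the IV. Study staff is thus a generic label and does not prove that one undivided team does everything. The designations in 4.7 may be neutral codes. The 5.7 key is a confidentiality device that links to identity and reveals dose only when joined to the 4.7 list. The text shows that role separation is not written down. It does not show that the blind is broken.

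**2. How much a dose blind protects SA1.** Documented inputs: 10 oral subjects (4.0, the target) and 8 infusion subjects (5.4), compared by independent-sample t-test. Assumptions: between-subject SD of 1; true method difference of 1 SD; 4 samples per visit average, with within-visit SD 0.5; no sampling noise on the infusion values; two-sided 5% level. At every oral visit one sample is dropped so that the visit mean moves closest to a target.

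Anchor without sampling noise: df = 10 + 8 − 2 = 16, noncentrality = 1 × √(10 × 8 / 18) = 2.108, power 0.508. Sampling noise raises the oral SD to √(1 + 0.5²/4) = 1.031, which fits the slightly lower simulated value in the first row below.

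A person who knows the dose steers toward that dose's infusion mean. A person blind to dose still knows the sample is oral and can steer toward the midpoint of the two infusion means. Results for the blinded person are averaged over both doses. The gap between the infusion means is assumed, in between-subject SDs.

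| Sample handling | Chance of detecting the difference | Repeat run |
|---|---|---|
| No sample dropped | 49.8% | 49.6% |
| Dropped, dose known | 43.2% | 42.9% |
| Dropped, dose hidden, gap 0.5 | 43.5% | 43.3% |
| Dropped, dose hidden, gap 1 | 44.1% | 44.3% |
| Dropped, dose hidden, gap 2 | 46.4% | 46.5% |

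In the main run the loss with dose known is 49.8 − 43.2 = 6.6 points. Hiding the dose recovers 43.5 − 43.2 = 0.3, 44.1 − 43.2 = 0.9, or 46.4 − 43.2 = 3.2 points. The share of the loss that remains is 6.3/6.6 = 95%, 5.7/6.6 = 86%, or 3.4/6.6 = 52%. The repeat run (20,000 trials) recovers 0.4, 1.4 and 3.6 of 6.7 points. Monte Carlo error on one rate at that size is about √(0.25/20,000) = 0.35 points.

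**3. Late regrouping.** Each completer takes one amount at Visit 2 and the other at Visit 3 (4.5), so regrouping changes order and not who receives which dose. Suppose Visit 3 values differ from Visit 2 values by π. The mean for a dose contains π times the share of completers taking that dose at Visit 3: 0.5π when orders are balanced. If losses leave 5 and 3 completers in the two orders, the share is 5/8 = 0.625 or 3/8 = 0.375, a shift of 0.125π. The comparator is external, so even perfect balance leaves 0.5π in the oral mean. Section 5.4 plans no low-versus-high test, which is where order balance would matter.

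**The case for a change.** The strongest opposing case is that a protocol claiming a double blind should say who is blinded and how. Here every step that reveals dose is assigned to an undefined group, the person who weighs the product must know the amount, and a few sentences would settle it. The reference to lab staff in 4.6 suggests a separation but does not create one. At an assumed gap of 2 SD, a dose blind would recover about half of the simulated loss, and averaging over doses hides the fact that the midpoint target pulls one dose less and the other more.

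Much of this stands as description: the separation is undocumented and the regrouping has no stated rule. It does not show that the oral-versus-infusion conclusion is at risk. The simulation is close to a worst case, with one sample steered at every visit of every oral subject. The steering becomes possible because 5.4 is silent on sample selection. That is a separate question about 5.4, and it remains whether or not dose is hidden. The outcomes are laboratory measurements, and plasma amino acid concentrations (5.3) may hint at the amount even under coding, which limits what stricter roles could deliver. A person kept apart from recruitment, assays and calculations may also mean extra staff in a pilot of up to ten subjects. The documents give no staff numbers.

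**Conclusion.** The concern does not call for a change. The sections leave a detail unwritten that a team running coded samples can fill sensibly: those who prepare the product do not compute the kinetics, and dose is revealed once the coded values are final. The text does not contradict such an arrangement.

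The gain from writing it down is small. Under the stated assumptions, full dose blinding recovers between 0.3 and 1.4 of about 6.6 points of power at gaps up to 1 SD, and 3.2 to 3.6 points at a gap of 2 SD. The variances, samples per average, method difference and gap are all assumed, so these figures show proportion and are not estimates for this trial. That every sample in this study is known to be oral does not depend on them. The regrouping limb reaches SA1 only through a fraction of any visit effect (0.125π in the example) and affects no planned test. Followed as written, the plan's oral-versus-infusion conclusion would not materially differ.

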#### **4.7 Randomization**

SP grouping will be predetermined before the first enrollment takes place. Study staff will document enrollment information into a spreadsheet that contains the SP group designations. SP labels will contain these designations. In the event that subject dropouts or screening failures skew the balance of groups, the groups will be modified toward the end of the enrollment period so that balance will be regained at the conclusion of the study.

#### **4.8 Study Products**

SP arrives packaged in a small tub. It is stored at room temperature. Study staff will weigh the doses of SP: 6.3g and 12.6g. Prior to ingestion, SP is dissolved into approximately 120mL of cool water. This product has been approved and used in previously approved studies (IRB#217658). It is provided at no cost by Adesso, LLC (Delaware).

---

### **5.0 Data and Specimen Collection and Management**

---

#### **5.1 Blood Sample collection**

Study staff will collect approximately 2mL of whole venous blood at each occasion and place it into an EDTA tube. A total of 15 blood samples per study visit will be drawn for this study. Approximately 60 mL of blood will be drawn per subject if they complete both visits 2 and 3.

## **5.2 Sample Storage**

Blood samples will be kept frozen at -80 degrees Centigrade or colder once the initial processing has taken place. Samples shall be stored in appropriate freezers in PI's laboratory, located in a restricted area inside the UAMS RIOA building. Said freezers are monitored continuously for proper temperature and working condition. Samples will be destroyed only after all data has been analyzed. All blood samples are coded using a unique identifier. None of a subject's personal identifiers are present on any biological sample.

## **5.3 Sample Analysis**

Plasma samples are analyzed for amino acid concentrations and stable isotope levels (enrichment). The analyses are performed in the CTRAL by study staff.

## **5.4 Data Analysis & Statistics**

Separate independent sample t-tests will be used to evaluate the difference in average whole-body protein metabolism measured using stable isotope infusion versus oral sipping feeding method for both the low- and high-dose supplement. To assess validity of the oral method compared to the infusion method, total error (TE), standard error of the estimate (SEE), and Pearson's correlation coefficient, in addition to mean difference and 95% limits of agreement (LOA), will also be evaluated for PS, PB, and NB. Data using the infusion method was collected on a previous cohort of participants of similar demographics (n=8; 60% female; Age=21.4  $\pm$  0.5 years; Weight=73.8  $\pm$  4.8 kg; percent body fat=21.1  $\pm$  2.2%) using the same supplement product and dosing (4).

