### 2.0 Background

---

Stable isotope tracers are routinely used to study protein metabolism in free-living individuals in the fields of nutrition and exercise (1, 2). Whole-body rates of protein synthesis (PS), breakdown (PB), and net balance (NB) in response to nutrition and exercise interventions are commonly evaluated using a primed-constant infusion of essential amino acid (EAA) tracers, typically  $^{2}\text{H}_5$ -phenylalanine and  $^{2}\text{H}_4$ -tyrosine (1). This method has many advantages. The primed-constant infusion allows for determination of basal protein kinetics, in addition to the acute physiological response to an intervention, which allows for each subject to serve as their own control. Although an effective method, administration of the primed-constant infusion requires involvement from multiple trained individuals, including research pharmacists and nurses who compound and administer the EAA tracer. This limits the ability to apply these methods in field-type settings outside of a hospital or lab. The cost associated with purchase and

compounding of the tracer, in addition to involvement from multiple specialists, makes these types of studies very expensive and difficult to conduct.

An alternative to primed-constant infusion is to orally ingest amino acid tracers in sip fashion to achieve a similar plateau enrichment. Oral bolus ingestion of amino acid tracer has been used to quantify 24-hour whole-body protein metabolism in a variety of healthy and clinical populations for over 50 years (3). This method is one of the most conducive field-methods for determining whole-body protein metabolism in free-living subjects and has minimal participant burden. However, full integration of the tracer from a single bolus ingestion into the entire protein pool takes at least 10 hours. This limits the ability to quantify acute changes in protein kinetics of acute exercise or nutritional interventions. However, ingestion of a priming bolus, followed by continuous ingestion of EAA tracer may achieve steady-state equilibrium similar to constant infusion of the isotope. Thus, oral ingestion may enable the determination of acute changes in protein kinetics in the same respect as constant infusion. If shown to be valid, this method would significantly reduce the rigor and expense of pharmacy-prepared infusions, and more importantly, allow for quantification of acute physiological protein responses within the field setting.

---

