### **3.0 Specific Aims**

---

SA1: To evaluate the validity of a continuous oral sip-feeding method of stable isotope tracer for the evaluation of whole-body protein metabolism in response to two different doses of an EAA/whey protein supplement (Low=6.3g and High=12.6g). We will compare kinetic responses with oral isotope ingestion to those previously determined by constant infusion with the same SP (4).

---

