### **4.0 Study Population**

---

Up to 10 subjects of any gender or ethnicity will be enrolled with a target of n=10, 50% female for study completion. Subjects' duration of participation is approximately 2 weeks.

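### Section 5.4 sets no acceptance value for any validity statistic, and its only hypothesis test looks for a difference, so no result is pre-specified as showing that the oral method is valid

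*Combined protocol and SAP*

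**What the plan says.** Section 3.0 states a single aim: "To evaluate the validity of a continuous oral sip-feeding method of stable isotope tracer", at two supplement doses, by comparison with earlier constant-infusion results. Section 2.0 makes the practical benefit depend on the outcome: "If shown to be valid, this method would significantly reduce the rigor and expense of pharmacy-prepared infusions".

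Section 5.4 is the only statistics section. Its first sentence gives the hypothesis tests: "Separate independent sample t-tests will be used to evaluate the difference in average whole-body protein metabolism", infusion versus oral, separately for the low and high dose. Its second sentence lists the validity statistics: "To assess validity of the oral method compared to the infusion method, total error (TE), standard error of the estimate (SEE), and Pearson's correlation coefficient". That sentence goes on to name two further measures, the average difference between methods and the 95% limits of agreement, each for protein synthesis, breakdown and net balance.

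The two sets of data come from different people. For the oral method, Section 4.0 says "Up to 10 subjects of any gender or ethnicity will be enrolled with a target of n=10, 50% female for study completion". For infusion, Section 5.4 says "Data using the infusion method was collected on a previous cohort of participants of similar demographics (n=8; 60% female" (the bracket continues with age, weight and body fat). The Study Calendar has no infusion visit.

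The document gives no alpha, power, SD, margin or maximum acceptable bias. It sets no limit for total error, standard error of the estimate, correlation or width of the limits of agreement, and no rule that links a result to a conclusion about validity.

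**The concern.** A validity aim asks whether two methods give close enough values. A t-test for a difference takes equality as its null hypothesis, so it can produce evidence against agreement but not for it. Failing to reject may mean that the methods agree, or only that the comparison was too imprecise to show that they do not. Fewer subjects or a noisier assay make the second explanation more likely.

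The other statistics could have supplied a criterion, but none carries an acceptance value. Total error, standard error of the estimate, correlation and limits of agreement are also built from pairs of readings on the same person. With two separate cohorts there are no such pairs, and only the difference in means can be estimated.

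At stake is the interpretation of the sole aim. A materially biased oral method could be reported as not different from infusion. An accurate one would have no pre-stated standard to meet.

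**Working it through.** The plan states no power, margin or SD, so there is no figure of its own to reproduce. Results are in units of the between-subject SD, or over a range of assumed CVs.

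**Inputs**
- Oral subjects: 10, the completion target in Section 4.0.
- Infusion subjects: 8, from Section 5.4. Whether all 8 contribute at each dose is not stated; 8 is assumed, with 4 as a low case.
- Alpha: not stated; two-sided 0.05 is assumed.
- SD: not stated; assumed equal in the two cohorts.

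**Precision**
- SE = sqrt(1/10 + 1/8) = sqrt(0.225) = 0.474 SD.
- Degrees of freedom = 10 + 8 - 2 = 16, and t(0.975, 16) = 2.120.
- 95% CI half-width = 2.120 × 0.474 = 1.01 SD.

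**Chance that the t-test misses a real bias** (noncentral t, noncentrality = bias / 0.474)
- Bias 0.5 SD: noncentrality 1.05, power 17%, missed 83%.
- Bias 1.0 SD: noncentrality 2.11, power 51%, missed 49%.
- Power of 80% needs a bias of 1.42 SD.
- With 6 oral versus 8 infusion, a 1-SD bias is missed 60% of the time. With 10 versus 4, it is missed 66% of the time.

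**Effect of noise on the t-test.** Hold the bias at 1 unit with 10 versus 8. The chance of a non-significant result is 2% at SD 0.5, 49% at SD 1, 83% at SD 2 and 90% at SD 3.

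**The t-test and a margin-based rule over the same CVs.** The second column takes a true 20% bias, so bias in SD units = 0.20/CV. The third column is the chance that a 90% Welch CI for the ratio lies wholly inside 0.80 to 1.25 when the true ratio is 1. It was simulated on the log scale with 10 versus 8. That margin is illustrative only.

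| Assumed CV | 20% bias non-significant | 90% CI inside 0.80 to 1.25, true ratio 1 |
|---|---|---|
| 10% | 2% | 99.5% |
| 12% | 9% | 96% |
| 15% | 25% | 82% |
| 20% | 49% | 46% |
| 25% | 65% | 18% |

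As the data become noisier, the t-test is more likely to overlook the bias, while the margin rule is more likely to return an inconclusive result. At a true ratio of 1.25, the margin rule wrongly declares similarity no more than 5% of the time at every CV in the table.

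The third column is per endpoint. If PS and PB at both doses all had to pass and were independent (an assumption), power at CV 15% would be 0.823^4 = 46%.

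**The case against.** The strongest reply is that Section 5.4 does not leave validity to the t-tests. Its second sentence gives that job to five other statistics, including limits of agreement, and noise counts against the oral method there because it widens the limits and raises total error and standard error of the estimate. This stands. The point about noise applies to the t-tests only, and it would be wrong to say that the plan contains no agreement statistics. What is missing is an acceptance value for any of them and, except for the mean difference, the paired data they need.

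A reader might infer that the plan treats p above 0.05 as proof of validity. No section says so. It is a natural reading of a difference test placed under a validity aim, but it is not a stated rule. A reader might also infer that no result could ever show validity. The documents support only the narrower statement that no result is pre-specified as doing so.

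Section 1.0 calls this a pilot of up to ten subjects, and estimation is a legitimate goal for a pilot. That softens the consequence but supplies no criterion, and the stated purpose remains to evaluate validity. If only estimates are intended, the text should say so.

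**Conclusion.** The point holds in this form: the only planned hypothesis test cannot provide evidence of agreement, no validity statistic has an acceptance value, and four of the five listed need pairing that the design lacks. With 10 versus 8, the comparison resolves mean differences only to about ±1 SD, so a non-significant result would leave biases of 0.5 to 1 SD quite possible.

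The SD-unit figures assume two-sided 0.05, equal SDs and all 8 infusion subjects at each dose; fewer subjects make them worse. The percentage-bias figures also depend on assumed CVs, because the documents give none. The absence of a criterion depends on none of these assumptions.

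**What to change.** In Section 5.4, replace the t-test sentence with the following content.

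- At each dose, report the oral/infusion ratio of means for PS and PB (analysed on the log scale) and the oral-minus-infusion difference for NB, with 90% Welch confidence intervals.
- Conclude that group means are similar only if the 90% CI lies wholly inside a margin that the sponsor has justified. The range 0.80 to 1.25 for PS and PB is only a starting point for discussion and has no basis in the documents. The NB margin is for the sponsor to set.
- Fix the margins before any oral-method result is available. Fixing them before unblinding is not enough: under Section 4.6 the blind covers the supplement amount, not the tracer method, and it is lifted only after data analysis.
- State that a non-significant difference is not evidence of validity, and that a CI crossing the margin is inconclusive.
- State that the conclusion concerns group means in two different cohorts, not within-person agreement. Amend the sentence on total error, standard error of the estimate, correlation and limits of agreement to match.
- If no margin can be justified, label the pilot results as estimates only.

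The cost is a paragraph of text and an agreed margin, with no new subjects or assays. The downside is that an inconclusive result is likely if variability is high. For the illustrative margin, per-endpoint power falls below one half at a CV of 20%, and it is lower still if several endpoints must all pass.

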## Study Schema

Study staff will recruit subjects via word of mouth to friends, family and colleagues.

Informed consent process takes place during Visit 1, followed by DXA scan.

Randomized subjects undergo two separate 7-hour study visits.

Visits 2 and 3 entail serial blood sampling from an IV catheter, ingestion of stable isotopes of amino acids every 10 minutes, and ingestion of SP (study product or placebo).

Blood samples analyzed at completion of study visits.

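### Total error, SEE, Pearson's r and limits of agreement need both methods measured in the same person, but the infusion data come from a different cohort

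*Combined protocol and SAP*

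**What the plan says.** The only aim is to validate continuous oral sipping of tracer against constant infusion. Section 3.0 takes the comparator from earlier work: "We will compare kinetic responses with oral isotope ingestion to those previously determined by constant infusion with the same SP (4").

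Section 5.4 plans two kinds of analysis for that comparison.

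- For group averages, at each supplement dose: "Separate independent sample t-tests will be used to evaluate the difference in average whole-body protein metabolism" between infusion and oral sipping.
- For validity, for PS, PB and NB: "total error (TE), standard error of the estimate (SEE), and Pearson's correlation coefficient, in addition to mean difference and 95% limits of agreement (LOA").

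The same section gives the origin of the reference values: "Data using the infusion method was collected on a previous cohort of participants of similar demographics", with n=8. The oral cohort is set in section 4.0: "Up to 10 subjects of any gender or ethnicity will be enrolled with a target of n=10".

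The visit descriptions show what each participant contributes. The Study Schema says "Visits 2 and 3 entail serial blood sampling from an IV catheter, ingestion of stable isotopes of amino acids every 10 minutes". Section 4.5 adds "All study procedures undertaken during Visit 2 will be repeated at Visit 3, with subjects ingesting the remaining SP amount". The crossover therefore varies the amount of supplement and not the tracer method.

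**The concern.** Section 5.4 assumes two incompatible data structures. The t-tests treat the oral and infusion data as independent groups. Total error, SEE, r and the limits of agreement treat them as two columns measured on the same people. Only the first matches the design.

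The protocol schedules no infusion visit. It does not say that the earlier participants will be re-enrolled, and it gives no matching rule or other unit of pairing, such as group means by time point. An analyst following section 5.4 would have to line up the rows arbitrarily. The value of r would then depend on row order. The limits of agreement, total error and SEE would reflect mainly how much people differ from one another. A good oral method could look invalid, or a poor one could look acceptable by chance. These are the statistics the plan names for assessing validity, so the main conclusion is at stake.

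The mean difference in the same list is not affected. It can be estimated from two separate cohorts.

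**Working it through.** **Inputs from the documents.** Infusion n=8 (section 5.4); oral n up to 10, target 10 (section 4.0); oral tracer at both Visits 2 and 3 (Study Schema, section 4.5). The documents give no SDs for PS, PB or NB, no margin and no acceptable width for the limits, so there is no stated figure to reproduce.

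**Assumptions for size only.** Results are in between-subject SD units, with normal data, equal SDs in the two cohorts and no bias between methods.

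**1. What each statistic needs.** Let d = oral − infusion in one person.

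- Limits of agreement = mean(d) ± 1.96 × SD(d)
- Total error = √mean(d²)
- SEE = residual SD from regressing one method on the other
- r = Cov(oral, infusion) / (SD × SD)

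All four involve the within-person covariance, because Var(d) = Var(oral) + Var(infusion) − 2 Cov. Two separate cohorts give the two variances and carry no information on Cov.

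**2. Number of possible pairings.** Assigning 8 of 10 oral subjects to 8 infusion subjects can be done in 10!/2! = 1,814,400 ways, each leaving out two oral subjects.

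**3. What r becomes.** For 8 unrelated pairs, the central 95% range of r is ±t/√(t² + 6), with t = 2.447 on 6 degrees of freedom: 2.447/√11.99 = 0.71. So r runs from about −0.71 to +0.71 with mean 0, whatever the accuracy of the method. In simulated data sets of this size (10 oral, 8 infusion), 500 random re-pairings of the same data moved r on average between about −0.88 and +0.88.

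**4. What the limits and total error become when both methods are perfect and identical.** With Cov = 0, SD(d) = √2.

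- Limits of agreement: ±1.96 × √2 = ±2.77
- Total error: √2 = 1.41 as a population root mean square; its average in samples of 8 is 1.37

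The correct value for both is zero.

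**5. Comparison with real pairing.** If the true within-person correlation is ρ, the correct half-width is 1.96 × √(2(1 − ρ)).

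| ρ (assumed) | Correct half-width | Unpaired half-width | Ratio |
|---|---|---|---|
| 0.9 | 0.88 | 2.77 | 3.2 |
| 0.7 | 1.52 | 2.77 | 1.8 |

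**6. Can the statistics tell a good method from a poor one?** The next table gives simulation averages (20,000 replicates) with within-person error SD e in each method. It compares 10 same-person pairs with 8 arbitrary pairs.

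| e (assumed) | r, same person / arbitrary | Limits half-width | Total error | SEE |
|---|---|---|---|---|
| 0.10 | 0.99 / 0.00 | 0.27 / 2.68 | 0.14 / 1.38 | 0.14 / 0.97 |
| 0.25 | 0.93 / 0.00 | 0.67 / 2.75 | 0.34 / 1.41 | 0.34 / 0.99 |
| 0.50 | 0.78 / 0.00 | 1.35 / 2.98 | 0.69 / 1.53 | 0.65 / 1.07 |

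With true pairs, a fivefold rise in error widens the limits fivefold (1.35/0.27 = 5.0). With arbitrary pairs it widens them by 11% (2.98/2.68 = 1.11).

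**The case against.** Several points can be made for the plan.

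- **It is a pilot, and the group comparison survives.** The t-tests come first in section 5.4, and section 3.0 promises only a comparison with earlier infusion results. This is true, and the mean difference is sound as a group-level quantity. But section 5.4 ties the assessment of validity to the paired statistics. Small size excuses imprecision; it does not excuse a statistic that fails to measure its target.
- **Some people might have both measurements.** The documents do not exclude earlier participants. Nothing provides for re-enrolling them either, 8 people could not fill 10 places, and the independent-sample tests would then be wrong.
- **The cohorts are similar.** Similar group averages do not supply a within-person covariance.
- **The sizes rest on assumptions.** This stands. The inflation ratio depends on the unknown true correlation: 3.2 or 1.8 in one set of assumptions, and about 10 for the limits at e = 0.10 in the other. With a large method bias, total error would partly reflect that bias. The loss of two oral subjects assumes that all 10 complete.
- **Visit 2 versus Visit 3 agreement is not validity against infusion.** This also stands. It measures repeatability and cannot replace the individual-agreement claim.

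**Conclusion.** The concern holds. Total error, SEE, Pearson's r and limits of agreement between oral and infusion cannot be computed meaningfully from this design, because the pairs they need do not exist. This follows from the documents alone.

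Under the assumptions stated, arbitrary pairing leaves r anywhere from about −0.71 to +0.71 and gives limits of about ±2.8 between-subject SDs even for a perfect method. The exact inflation cannot be determined from the documents. The analysis is wrong as written, not merely under-described, and it should be changed before any data are analysed.

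**What to change.** In section 5.4:

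1. Remove total error, SEE, Pearson's r and limits of agreement for oral versus infusion.
2. For that comparison, report the unpaired difference in means and the ratio of SDs, with confidence intervals, for PS, PB and NB at each dose. Either pre-specify an equivalence margin or present the result as estimation only; a non-significant t-test does not show agreement. With 8 and 10 subjects and a common SD, the 95% interval for a difference in means is about ±2.12 × √(1/8 + 1/10) = ±1.01 SD, so the group comparison will be imprecise. It also remains confounded with differences between cohorts.
3. Apply paired statistics (mean difference, limits of agreement, total error, within-subject SD or ICC) to each subject's basal PS, PB and NB before the supplement at Visit 2 versus Visit 3, labelled as repeatability of the oral method. Section 4.5 places the supplement about three hours after the start at both visits. Section 5.1 gives 15 samples per visit without times, so confirm that enough fall before the supplement.
4. State that individual-level agreement with infusion is not assessed, and narrow the validity wording in sections 1.0 and 3.0 to match.

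The cost is rewording, with no new visits or samples. The price is a narrower claim: group-level comparison plus repeatability. If individual agreement is essential, both tracer methods must be measured in the same participants, which means adding infusion visits.
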